September 26, 2021

**Evaluation of Plasma Cholecystinin (CCK) Levels and Gallbladder (GB) Functions in
Hyperemesis Gravidarum**

NCT 03950167.

Background: The pathophysiology of hyperemesis gravidarum (HG) remains poorly understood. A multifactorial origin, including infective, anatomical and psychological factors, and hormonal changes of pregnancy has been proposed. Altered cholecystinin (CCK) levels may have potential consequences on gastric emptying, which may be related to nausea and vomiting. In this context, alterations in CCK secretion in women diagnosed with HG have been previously reported, and alterations in CCK levels lead to impaired gallbladder (GB) functions.

Objective: In this study, we aimed to evaluate fasting and post-prandial CCK levels, and GB function in HG patients.

Design: Prospective cohort study

Methods: HG patients who present before the end of the 14th week of gestation at our obstetrics outpatient clinic, with persistent vomiting and routine prenatal visits, will be recruited. The required evaluations, including the collection of venous blood samples and sonographic evaluation of GB functions, will be performed at the initial assessment.

After a 12-hour overnight fasting period, venous blood samples will be collected for routine haematological, biochemical, hormonal tests and CCK levels. Transabdominal ultrasonography (US) will be performed to assess GB functions. Subsequently, a fatty test meal (100 g of milk chocolate) will be administered to the patients. The postprandial CCK concentrations at 15 min after meal intake will be measured. The postprandial GB volume (PGv) will be measured using the same US equipment by the same radiologist for each patient at the 45th minute after the meal

Statistical analysis:

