Statistical analyses will be performed using SPSS for Windows, version 22.0 (SPSS Inc., Chicago, IL, United States). Since this is the first study comparing both CCK levels and GB functions in patients diagnosed with HG and healthy pregnant women, a power analysis is not feasible. The distribution of continuous variables (normal or skewed) will be determined with the Shapiro-Wilks test. Levene's test will be used for the evaluation of the homogeneity of variances. Unless specified otherwise, continuous data will be described as mean \pm SD for normal distributions, and median (inter-quartile range) for skewed distributions. The two groups will be compared with Student's t-test for normally distributed variables and the Mann-Whitney U test for the data that were not normally distributed. Degrees of relation between the variables will be evaluated with the Pearson or Spearman correlation analysis. A p value of <0.05 will be accepted as significant in all statistical analyses.

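### The HG-versus-healthy comparison is unadjusted, so a difference in gestational week between the groups, if week is related to the outcome, could be reported as an HG effect

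*Combined protocol and SAP*

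**What the plan says.** The Design line reads "Prospective cohort study", so HG status is observed and not allocated. The Statistical analysis section describes the work as the "first study comparing both CCK levels and GB functions in patients diagnosed with HG and healthy pregnant women". The two groups are to be compared by Student's "t-test for normally distributed variables and the Mann-Whitney U test for the data that were not normally distributed". The only other analysis of how variables relate is bivariate: "Degrees of relation between the variables will be evaluated with the Pearson or Spearman correlation analysis". No regression, covariate list, stratification or matching is described.

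Methods sets the gestational limit in a sentence whose subject is the HG group: "HG patients who present before the end of the 14th week of gestation at our obstetrics outpatient clinic". Each woman is measured once, at her first assessment, so the week of measurement can vary. No separate window or set of procedures is clearly given for the healthy women. The meal, for example, is described this way: "a fatty test meal (100 g of milk chocolate) will be administered to the patients".

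**The concern.** The study asks whether CCK and gallbladder function differ in HG. Women with HG are recruited with persistent vomiting, and healthy women would attend for other reasons. Nothing in the plan makes the two groups' gestational weeks agree. If they differ and an outcome changes with week, the two-sample test estimates the HG effect plus a week effect and cannot separate them.

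The planned correlations could show that week is related to an outcome, but they do not correct the group contrast. The normality and variance checks concern the shape of the data, not whether the groups are comparable. An upper limit of week 14, even if it applies to both groups, restricts the imbalance without forcing it to zero. At stake is a significant difference attributed to HG that partly or wholly reflects stage of pregnancy. A real difference could equally be masked.

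**Working it through.** The plan gives no sample size, SD, effect size or power, so there is no figure of its own to reproduce. What follows is an illustration under stated assumptions.

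**Inputs from the documents.** Two non-randomised groups; unadjusted t-test or Mann-Whitney; significance at p < 0.05 (sidedness not stated, two-sided assumed); HG patients limited to week 14.

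**Assumptions.** No true HG effect; linear week effect; within-group correlation between week and outcome r = 0.2 to 0.4; shift in mean week between groups D = 0.25 to 1.0 within-group SDs; n = 20, 30 or 40 per group.

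**Step 1: bias.** In outcome SDs, the unadjusted difference is off by d = r × D. The sample size does not enter. If r = 0 or D = 0, d = 0 and the test keeps its 5% level.

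**Step 2: rejection rate of the t-test.** Noncentral t with noncentrality d × √(n/2) and 2n − 2 degrees of freedom. For example, with n = 30, r = 0.4 and D = 1.0, d = 0.40, the noncentrality is 0.40 × √15 = 1.55 with 58 df, and the rejection rate is 33.2%.

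| Shift D (SD of week), n = 30 per group | r = 0.2 | r = 0.4 |
|---|---|---|
| 0.25 | 5.4% | 6.7% |
| 0.50 | 6.7% | 11.9% |
| 0.75 | 8.8% | 20.8% |
| 1.00 | 11.9% | 33.2% |

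Over the same grid the range is 5.3% to 23.4% at 20 per group and 5.6% to 42.4% at 40 per group.

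**Step 3: effect of sample size.** At D = 1 and r = 0.3, the rate is 15.2% at 20 per group, 26.3% at 40 and 56.0% at 100. The bias stays fixed while the standard error shrinks, so a larger study is more likely to declare the spurious difference significant.

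**Step 4: alternatives, simulated at 30 per group.** Mann-Whitney rejects 4.7% to 30.9% of the time, so switching to the rank test gives no protection. A linear model with group and week rejects 4.8% to 5.1%.

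**Step 5: both groups inside one window.** Suppose all women lie between weeks 6 and 14 (the lower bound is assumed), with a within-group SD of about 1.8 weeks and 30 per group.

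| Difference in mean week | D | Unadjusted, r = 0.2 | Unadjusted, r = 0.4 |
|---|---|---|---|
| 0.5 | 0.28 | 5.6% | 7.1% |
| 1.0 | 0.56 | 7.4% | 14.1% |
| 1.5 | 0.85 | 9.9% | 25.4% |

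The week-adjusted model gives 4.8% to 5.2% throughout.

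**Step 6: price in precision.** The large-sample ratio of adjusted to unadjusted SE is √((1 − r²)(1 + D²/4)).

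- At D = 1: r = 0.2 gives √(0.96 × 1.25) = 1.10, and r = 0.4 gives √(0.84 × 1.25) = 1.02. Simulated at 30 per group: 1.11 and 1.04, and 1.13 if week is unrelated to the outcome.
- At D = 0: √0.96 = 0.98 and √0.84 = 0.92. Simulated: 0.99 and 0.93, a small gain.

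**The case against.** The strongest reply is that neither premise is in the documents. They do not show that the groups differ in week, or that CCK or gallbladder volume changes with it. Any unadjusted observational comparison could be criticised in the same way, and week is only one possible confounder. This stands, and it is why the point is conditional. It does not excuse a plan that has no protection if both conditions hold, because the plan cannot know in advance that they will not.

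A second reply is that the recruitment sentence also mentions routine antenatal attendance, so the week-14 limit may cover both groups. Matching may also be done in practice without being written down. Both are possible. A shared limit makes large shifts less likely, but the shared-window table shows it does not rule out inflation.

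A third reply is that the range is selective. Taking r = 0.2, 0.3 and 0.4 with the four shifts at 30 per group, 8 of 12 combinations stay below 12%. Linearity also matters. In the shared window with r = 0.4 and means 1.5 weeks apart, a separate simulation of 8,000 runs gave an unadjusted rate of 26% for a linear effect, 17% if the effect levels off at week 9, 14% if it peaks at week 9, and 5% if it peaks at week 10. This weakens the upper figures but not the remedy: the adjusted model stayed between 4.5% and 5.9% across those runs.

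Finally, the stated objective is to evaluate, with no powered hypothesis, so an unadjusted contrast is a legitimate description. That is true of the description. The plan nevertheless applies a significance test to the comparison, and readers will take a significant result as a finding about HG.

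**Conclusion.** The concern holds, with medium confidence about its practical size. The only group contrast in the plan is unadjusted, in a non-randomised comparison, and nothing described controls gestational week. The actual bias is unknown. It is negligible for a small imbalance or a weak week effect; the largest rates in the grid arise only at its extreme corner, with r = 0.4 and a full SD between the groups. The figures rest entirely on assumed group sizes, correlations, shifts and a linear week effect. Week is the only confounder simulated, so the results show that adjustment removes that one source and nothing more. The point is worth fixing because it affects the study's central comparison and the remedy is cheap.

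**What to change.** In the SAP, make the main comparison of each CCK and gallbladder outcome a linear model with group and gestational week at measurement, on the log scale where the outcome is skewed. Report the adjusted HG-versus-healthy difference with its 95% confidence interval, and keep the t-test or Mann-Whitney test as supportive. In Methods, state the gestational window and measurement procedures actually planned or used for the healthy women.

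The change is a few lines of wording, and SPSS fits the model. Week is already needed to apply the limit to HG patients; that it is also recorded for the healthy women is an assumption to confirm. The model spends one degree of freedom and loses some precision if the groups differ in week: at a 1 SD difference the SE is 4% to 11% larger, or 13% if week proves unrelated to the outcome. It does not protect against other confounders. If the healthy women's window or procedures differ from those of the HG patients, describing them makes the difference visible but does not remove it.
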